6.4.2 Adverse events

MedDRA version 23.1 will be used for reporting of AEs. All summaries will be provided using SAF.

Statistical analysis plan	Date:	27-Oct-2023	
Trial ID: SU-G-01	Version:	1.0	
EudraCT No.: 2020-000455-12	Status:	Final	
CONFIDENTIAL	Page:	30 of 47	

6.4.2.1 Events of special interest

An AE is any untoward medical occurrence in a subject that does not necessarily have a causal relationship with the administered IMP. An AE is a TEAE if the time of onset is on or after the time of the first dose administration of IMP and, no later than seven days seven days after the last dose administration of IMP. Selected (non-serious or serious) AEs are considered ESIs. ESIs are events that are considered critical for the evaluation of the product's safety profile and for which additional data was collected. ESIs for this trial are:

- Systemic allergic reactions including anaphylaxis
- Events treated with adrenaline
- Severe local swelling of the mouth and/or throat
- Eosinophilic oesophagitis.

6.4.2.2 Reporting of adverse events

All TEAEs will be summarised by treatment group according to causality (IMP related or not), severity (mild, moderate, severe), seriousness (yes/no), action taken, outcome (recovered or resolved / recovered or resolved with sequelae / not recovered or not / resolved / fatal / unknown), and whether the event led to IMP discontinuation and interruption. The number of subjects in treatment group, the frequency and proportion of subjects having the event, as well as the number of events and proportion of events will be displayed. A similar summary table will be produced for all IMP-related TEAEs.

All TEAEs and all IMP-related TEAEs will be summarised (in separate tables) by treatment group, SOC, and PT, displaying number of subjects in treatment group, and number and frequency of subjects having the event. The tables will be sorted according to most frequent SOC and PT in the active treatment group, and the most common TEAEs defined as those that are present in at least 2% of subjects in the active treatment group will be marked.

Severe TEAEs will be listed only if there are fewer than 10 events in total. Otherwise, severe TEAEs will also be summarised and presented by SOC and PT similar to how TEAEs are presented. The same follows for SAEs, TEAEs leading to IMP discontinuation, and IMP-related TEAEs leading to IMP interruption.

For most frequent IMP-related TEAEs (present in at least 2% of subject in the active treatment group) onset and duration will be presented as follows: time to onset and average duration both in days, will be presented by SOC and PT and treatment. In addition, for day 1 of treatment average time to onset in minutes will be presented by SOC PT and treatment.

In addition, most frequent non-serious TEAEs reported in at least 5% of subjects in any treatment group by SOC and PT.

For the most frequent IMP-related TEAEs which are recurrent, the average daily duration and the average duration in days from first to last occurrence will be presented by PT and treatment.

A table with the overall summary of the safety profile will be produced showing number of subjects with TEAEs, IMP-related TEAEs, IMP-related severe TEAEs, IMP-related treatmentemergent SAEs, IMP-related TEAEs leading to IMP discontinuation and each type of IMPrelated treatment-emergent ESI by treatment group.

Serious TEAEs, severe TEAEs, TEAEs leading to IMP discontinuation, IMP-related TEAEs leading to IMP interruption, individual ESIs, TEAEs, and all non-treatment-emergent AEs for the total analysis set will be listed. Medication errors will also be listed. Pregnancies will be listed if fewer than 10 cases have been reported; otherwise summarised.

 Date:
 27-Oct-2023

 Version:
 1.0

 Status:
 Final

 Page:
 31 of 47

6.4.3 Additional safety assessments

Shift tables will be produced for clinical laboratory assessments (haematology, blood chemistry and urinalysis) assessments including the categories low, normal, high, and missing as relevant, where the shift table will include the categories normal, abnormal not clinically significant, and abnormal clinically significant.

Vital signs and the pulmonary function test parameters (FVC, FVC percent predicted, FEV₁, and FEV₁ percent predicted) will be summarised by visit and treatment group.

Findings of urine pregnancy test will be summarised in a listing.

6.5 Changes and/or deviations to protocol-planned analyses

Several changes were made to the statistical analysis described in the trial protocol. The list of changes is summarised in this section:

- PP analysis set is removed from analysis sets used in this trial. This analysis set does not align with the estimand framework; therefore, it will not be used in this trial.
- Safety and tolerability objectives and endpoints are added as supportive secondary endpoints.
- As described in the estimand framework, the most important IE is the discontinuation of IMP. The IMP discontinuation was not collected in the relevant manner in eCRF. Discontinuation of IMP is then re-classified based on reported IMP discontinuation and trial withdrawal reason (see Section 6.1.2), and these re-classified reasons are used in the estimand framework.
- In this trial, subjects were stratified based on their history of asthma in adulthood. During the trial, it was determined that it is most relevant for interpretation of the disease and treatment is ongoing asthma status at screening. Therefore, the asthma status at screening will be used in the analysis models instead of asthma strata. Twenty one subjects were stratified as asthmatics but did not have ongoing asthma at screening. Subjects with ongoing asthma are expected to be well-balanced between treatment arms.
- In the protocol, the primary and key secondary endpoint estimator contains the trial site/country as a random effect. In SAP, county and year interaction is a random effect. The change accounts for the variability of pollen load yearly in each country.
- In the protocol, the proposed MCID is 0,16. Since the protocol proposal, additional research was performed and based on published results presented new MCID for PGPS is 0,1 and EGPS 0,22 (**Blaiss et al. 2022**).
- Pollen season end date and pollen peak definition a modified to add clarity. Pollen season end date is specified that it is the last day of the last occurrence of 3 consecutive days with pollen count larger or equal to 10 grains/m³. For the peak season it is specified the 14 consecutive days period is used as a peak.

7 Sample size determination

General considerations

In this trial, primary and secondary endpoints will be tested hierarchically to control the familywise error rate at 5% level. Individual endpoint analyses will be based on treatment comparisons using a 2-sided t-distributed test on a 5% level of significance.

The power calculations were done in two steps. This sample size wasthen evaluated using the estimand framework. The power was calculated for both the primary endpoint (TCS) and the key secondary endpoint (RQLQ). It is expected that the treatment difference in overall RQLQ during peak season is greater than the MCID of 0.10 and during entire season greater than 0.22 (Blaiss et al. 2022).

TCS power calculation

The estimated TCS mean, standard deviation and treatment differences during the peak season from three trials is presented in Table 8. The power calculation is based on a TCS treatment difference of 21% (1.64 in absolute value) and a common standard deviation of 5.5. Under these assumptions, the trial has a power of 80% with the sample size of 180 evaluable subjects. The power is 86% for the primary estimand and 80% for the secondary estimand with the assumption that 10% out of 220 subjects will discontinue the trial, with 4.5% of subjects discontinuing due to AEs and 1% due to lack of efficacy each year.

Trial	Placebo $\mu(\sigma)$	Active $\mu(\sigma)$	Difference absolute (relative)
GT-08 2006	8.44 (5.48)	5.14 (4.06)	3.3 (39%)
P05238	7.74 (6.50)	6.10 (5.09)	1.64 (21%)
P08067	5.73 (5.03)	4.56 (4.60)	1.17 (20%)
Average			2.04

Table 8: Mean and standard deviation of TCS during the peak of a season.

RQLQ power evaluation

The estimated RQLQ mean, standard deviation and treatment differences during the peak season from 3 trials raw data is presented in Table 9 below.

Table 9: Mean and standard deviation of RQLQ during the peak of a season.

Trial	Placebo $\mu(\sigma)$	Active $\mu(\sigma)$	Difference Absolute (relative)
GT-08 2005	1.82 (1.11)	1.37 (0.97)	0.45 (25%)
GT-08 2006	1.48 (1.05)	1.05 (0.91)	0.43 (29%)
P05238	1.73 (1.34)	1.41 (1.12)	0.33 (18%)
P08067	1.73 (1.34)	1.18 (1.08)	0.15 (11%)
Average	0.34		

A common standard deviation of 1.15 has been assumed in the power evaluation. An expected placebo mean is 1.60 and an expected treatment difference is 0.34. With 180 evaluable

Statistical analysis plan
Trial ID: SU-G-01
EudraCT No.: 2020-000455-12
CONFIDENTIAL

subjects per treatment arm, the power of 98% is reached for testing if RQLQ treatment difference is greater than proposed MCID of 0.1. The power is 95% for the primary and 92% secondary estimands for the sample size of 220 subjects with the same discontinuation assumptions as for TCS.

Conclusion

The suggested sample size is 180 evaluable subjects per treatment arm. 220 subjects should be randomised in each arm, assuming a 10% discontinuation of subjects per year, where 1% discontinued due to lack of efficacy and 4.5% due to AEs. In such case, the trial has a power of at least 80% in order to detect a statistically significant difference of at least 21% with common standard deviation no larger than 5.5 for primary endpoint in observed case scenario. The trial has a power of 86% and 80% for primary endpoint for primary and secondary estimands respectively. Similarly, 95% and 92 % power for RQLQ for the primary and secondary estimand 0.1 in RQLQ for observed case.

8 Demographics and baseline characteristics

Summaries for numerical variables tables will display the descriptive statistics such as: mean, SD, median, min and max.

Summaries for categorical variables frequency tables will display counts and percentages.

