6.2 Randomisation

The randomisation list will be generated by a trial-independent statistician and will not be accessible to trial personnel involved in the conduct of the trial, until the database has been locked. The treatment allocation will be stratified based on pre-existing diagnosis of asthma in order to ensure equal treatment distribution of subjects with or without asthma.

The randomisation codes will only be made available for the trial data manager and statistician when the clinical database has been locked and all protocol deviations have been identified and evaluated.

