11.4 Medical history

The relevant medical history must be recorded in the eCRF.

The asthma history should include a detailed description of all asthma exacerbations including information on visits to emergency rooms, hospitalisations and changes in asthma treatment during the past 2 years.

In addition, a detailed allergy history including recording of the subject's history of rhinitis, conjunctivitis or rhinoconjunctivitis, atopic dermatitis and food allergy including start and stop date as well as cause of condition (if available). A subject should be stratified as asthmatic if they have been diagnosed and/or treated for asthma in adulthood.

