3.2 Study design

This is a phase III, randomised, parallel-group, double-blind, placebo-controlled trial of 5-grass mix SLIT-drops in adults with grass pollen-induced moderate to severe allergic rhinoconjunctivitis, with or without asthma. The trial was conducted over two grass pollen seasons.

A total of 440 adult subjects were planned to be randomised (1:1) to continuously receive either active treatment (grass SLIT-drops) or placebo treatment once daily

All subjects should receive daily treatment continuously from at least 16 weeks before the anticipated start of the 1st EGPS through the 2nd EGPS (definitions are provided in Section 9.1), corresponding to approximately 26 months of treatment (see Figure 1). Open-label rescue medication for AR/C was provided during the GPS. The subjects were asked to complete a RQLQ diary at V3 during the off-season for grass and tree pollen and then weekly during the EGPSs. The subjects were furthermore asked to fill in an eDiary daily during the EGPSs to capture information on rhinitis and/or conjunctivitis symptoms, use of symptom-relieving medications, and impact of rhinitis and/or conjunctivitis quality of life.

Figure 1 Trial design

Data for the primary endpoint were collected by the subjects by completing questions related to their daily symptoms and medication use in an electronic diary (eDiary).

No interim analysis was planned.

Routine safety surveillance was conducted throughout the trial. The follow-up visit was conducted via a telephone call approximately one week after the end of trial visit.

The first subject was randomised 15-Aug-2022 and subjects were planned to received treatment for 26 months. A total of 445 subjects were randomised and dosed.

Statistical analysis plan Trial ID: SU-G-01	Date: Version:	27-Oct-2023 1.0
EudraCT No.: 2020-000455-12	Status:	Final
CONFIDENTIAL	Page:	15 of 47

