3.2.3 Randomisation

The randomisation list was generated by a trial-independent statistician and will not be accessible to trial personnel involved in the conduct of the trial, until the database has been locked and all protocol deviations that have been identified, evaluated, classified, categorised and closed.

The randomisation was administered centrally via IRT and treatment allocation was stratified based on pre-existing diagnosis of asthma to ensure equal distribution of subjects with or without asthma across the treatments.

Randomisation errors

During the conduct of the trial, one randomisation error has occurred. An overview of the error can be found in supplementary document to the SAP: Documentation of Trial Analysis Sets. The randomisation error was included in the FAS. If missing data have occurred, it will be handled using the estimand framework.

4 Statistical hypotheses

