6.2 Analyses

The main estimator and sensitivity estimator for both estimands will be based on an identical method of statistical analysis .The estimator for all estimand will be based on MMRM with treatment, year, treatment and year interaction, and ongoing asthma status as fixed effects and country and year interaction as random class effect (more details specified Section 9.5.2). Exposure to pollen can vary yearly; thus, treatment effects may differ each year. Therefore, the model contains treatment and year interaction as a fixed effect. Pollen count depends on local geography and weather and can vary locally yearly. Thus, the model comprises country and year interaction as a random effect.

The actual data used in each analysis may vary according to the different strategies taken for the handling of IEs and missing data. In the trial product estimand, data until treatment discontinuation will be included in the analysis and treatment policy estimand all observed data will be included.

Imputations will be done on the average scores, but not daily/weekly values. To calculate an average score, only one observation is needed.

Missing data will be imputed by sampling from an appropriate pool that matches the subject's characteristics. Missing data for 1st year will be imputed from observed data in 1st year, and missing data for 2nd year will be imputed from the observed data in 2nd year. Thus, PGPS data will be imputed from observed PGPS data and EGPS from observed EGPS. Missing data for subjects with ongoing asthma will be imputed from subjects with ongoing asthma for subjects without ongoing asthma will be imputed from subjects without ongoing asthma following the rules defined below.

If the IE occurred after 1st season, then the missing data imputation in the 1st year will be handled disregarding the IE and imputed under assumption MAR (data will be imputed from the subject's own treatment arm for both estimands). The missing data of 2nd season will be handled based on IE. If IE occurred after 2nd, the missing data will be handled disregarding IE in both seasons. For more details, see Sections 6.2.1 and 6.2.2.

The imputation pool of subjects will consist of subjects with all and partially observed data. In other words, if subject will be used in the analysis, they will also be used in the pool of the subjects to impute from.

Rubin's (Rubin 1987) multiple imputation strategy will be used to pool results of multiple analysis.

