6.3.1.3 Symptoms-score tertiles analysis

Howarth *et al.* (2012) examined effects of allergen immunotherapy where study sites were grouped by the level of allergic rhinoconjunctivitis symptoms (low, medium, high) among placebo-treated subjects. The hypothesis was that sites where the symptoms scores were the highest under placebo, the seasonal disease activity was the highest and, presumably, therefore an effect of the allergen immunotherapy could potentially be greater here than at sites where the symptoms scores under placebo were lower.

To address this, trial sites will be grouped into tertiles according to the trial sites' placebo mean TCS in the PGPS based purely on observed TCS values (i.e. no imputation) for each of the two years (2022 and 2023), respectively. TCS and RQLQ will be analysed for the PGPS using the

Statistical analysis plan	Date:	27-Oct-2023	
Trial ID: SU-G-01	Version:	1.0	
EudraCT No.: 2020-000455-12	Status:	Final	
CONFIDENTIAL	Page:	29 of 47	

ALK

DPS1/on-treatment observation period data. The model(s) will be ANCOVAs run for each year separately. The model will include treatment, seasonal-disease-activity-subgroup and asthma strata as fixed effects and allowing unequal residual variances among the two treatment arms.

Treatment contrasts corresponding to each level of trial-site-subgroup will be output along with (multivariate) tests of (year-specific) subgroup effects: that is, for each year, whether the three treatment contrasts (corresponding to the three tertiles subgroups) are statistically significant from one another.

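### Minor, free improvement: add the asthma stratum used for randomisation to the confirmatory MMRM, alongside ongoing asthma at screening

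*SAP*

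**What the plan says.** Protocol 6.2 sets the stratification factor: "The treatment allocation will be stratified based on pre-existing diagnosis of asthma". Protocol 11.4 gives the rule for assigning it: "A subject should be stratified as asthmatic if they have been diagnosed and/or treated for asthma in adulthood". SAP 3.2.3 confirms that this was done: "The randomisation was administered centrally via IRT and treatment allocation was stratified based on pre-existing diagnosis of asthma".

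The protocol's model (15.11.1) has a yes/no asthma indication as a fixed effect and does not name the randomisation stratum. SAP 6.5 nevertheless treats its own choice as a change from the protocol: "the asthma status at screening will be used in the analysis models instead of asthma strata". The stated reason is that current asthma matters more for interpreting the disease and its treatment. SAP 6.5 also gives a count: "Twenty one subjects were stratified as asthmatics but did not have ongoing asthma at screening". For balance between arms on ongoing asthma, it offers only an expectation.

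The substitution runs through the confirmatory analysis. The MMRM in SAP 6.2 has "ongoing asthma status as fixed effects and country and year interaction as random class effect", and the imputation cells in SAP Tables 5 to 7 are defined by ongoing asthma. The stratum survives in one place, the supplementary tertile ANCOVA on observed data in SAP 6.3.1.3: "The model will include treatment, seasonal-disease-activity-subgroup and asthma strata as fixed effects".

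**The concern.** When randomisation is stratified on a factor, the usual practice is to adjust for that factor. Stratification balances it between arms. A model without it leaves its contribution in the residual variance, so the standard error is larger than the design warrants. Balance on ongoing asthma is not guaranteed in the same way.

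The factor has some history here. Protocol 1.4 reports that in the earlier placebo-controlled trial of the related 3-grass product, asthma was significantly more frequent in the active arm. A post hoc analysis of the subjects without asthma then gave a more favourable picture than the overall comparison. Stratified allocation is presented as a feature of the present trial.

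At stake are a little precision and the internal consistency of the SAP. SAP 6.5 speaks of the analysis models in general, while 6.3.1.3 still uses the strata. No pre-specified estimator of either estimand would show the primary result adjusted for the factor actually used in the allocation.

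**Working it through.** **Inputs from the documents.** Randomised: 445 (SAP 3.2, "A total of 445 subjects were randomised and dosed"). In the asthma stratum without ongoing asthma: 21 (SAP 6.5). Planned TCS difference 1.64, SD 5.5, 180 evaluable subjects per arm, power 80% (Protocol 15.2, SAP 7).

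**Assumed, because the documents do not give them.** Share of subjects in the asthma stratum: 20% (89 subjects) or 40% (178). Effect of asthma on TCS: 1, 2 or 4 points, driven either by the stratum or by ongoing asthma. Four points is 4/1.64 = 2.4 times the planned treatment difference, so it is a deliberately severe case.

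**1. The plan's own figure.** n per arm = 2(1.960 + 0.842)² × 5.5² / 1.64² = 177, against 180 stated. With 180 per arm, SE = 5.5 × √(2/180) = 0.580, 1.64/0.580 = 2.83, and power = Φ(2.83 − 1.96) = 80.8%. The stated 80% reproduces.

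**2. Subjects adjusted off-stratum.** 21/445 = 4.7%. This is a minimum, because the SAP does not say whether anyone in the non-asthma stratum had ongoing asthma. As a share of the asthma stratum, it is 21/89 = 24% or 21/178 = 12%.

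**3. Balance.** Under random allocation within the stratum, the 95% hypergeometric range for the number of the 21 in one arm is 6 to 14 (stratum of 89) or 6 to 15 (stratum of 178).

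**4. Effect on the standard error, by hand.** Suppose the stratum drives TCS with effect β and the model adjusts for ongoing asthma. The subjects classed as not asthmatic are then a mixture, with a fraction q from the asthma stratum. The average residual variance rises by β² q(1 − q) × (share of subjects in that class).
- 20% share: the class has 445 − 68 = 377 subjects and q = 21/377 = 0.0557. With β = 4 the increase is 16 × 0.0526 × 0.847 = 0.713. √((30.25 + 0.713)/30.25) = 1.012, so the SE is 1.2% larger.
- 40% share: the class has 445 − 157 = 288 subjects and q = 21/288 = 0.0729. The increase is 16 × 0.0676 × 0.647 = 0.700, again giving a 1.2% larger SE.
- With β = 2 and a 20% share, the increase is 0.178 and the SE is 0.3% larger.

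**5. Simulation.** N = 445, stratified blocks of 4, ANCOVA on one season with residual SD 5.5, complete data, 4,000 replicates for each of 12 scenarios.

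| | Adjusting for stratum | Adjusting for ongoing asthma (SAP) |
|---|---|---|
| Type I error | 4.6–5.3% | 4.5–5.5% |
| Power at 1.64 | 87.6–88.4% | 86.8–88.7% |
| Mean estimate under no effect | within ±0.011 | within ±0.012 |
| Model SE, stratum-driven effect 4, 20% share | 0.5209 | 0.5272 |
| Model SE, stratum-driven effect 4, 40% share | 0.5214 | 0.5274 |

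The Monte Carlo error is about 0.3 points for type I error and 0.5 points for power. The SE ratios are 0.5272/0.5209 = 1.012 and 0.5274/0.5214 = 1.012, which agree with step 4. The largest power loss is 87.68 − 86.82 = 0.9 points (40% share, stratum-driven effect of 4). If ongoing asthma is the true driver, the SAP's covariate is slightly better, by at most 88.65 − 88.08 = 0.6 points. Power differences of this size are close to the simulation noise.

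The simulation omits the country-by-year random effect, the second season, unequal variances and multiple imputation. It did not fit a model with both asthma terms.

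**The case against.** The strongest case for the SAP is that the change is disclosed and given a clinical reason, with the affected subjects counted. SAP section 3 states that the plan was approved before database lock and unblinding. The substitute is a pre-treatment variable closely related to the stratum, and it may be the more prognostic of the two. The protocol model never named the stratum. The tertile ANCOVA is supplementary and outside the testing hierarchy, so its wording may simply be left over. All of this stands, and it is why the point is minor.

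A reader might go further and infer one of three things that the documents do not support.

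- **That the analysis departs from the randomisation.** SAP 5.1 defines the FAS as all randomised subjects, analysed in their assigned arm. Only the covariate that represents asthma changes.
- **That changing a covariate during the trial threatens the type I error.** The choice was made blind and concerns a baseline variable. In the simulation the error stays at about 5%.
- **That the imputation cells should also be redefined by stratum.** This is a trade-off. The subgroup analysis in SAP 6.3.1.1 runs on imputed data and contrasts subjects with and without ongoing asthma. With stratum-based cells, 12% to 24% of the donors for a subject with ongoing asthma would not have it (step 2 of the working), which would blur that contrast. The current cells match the subgroup variable.

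The objection leaves two things unanswered. The stratum is available and could be added at almost no cost, and SAP 6.3.1.3 and 6.5 do not agree.

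**Conclusion.** The point holds as a minor, free improvement. At least 21 of 445 subjects (4.7%) are adjusted for in a category other than their stratum, and no main or sensitivity estimator for the primary endpoint uses the stratum. The treatment estimate is not biased and the type I error is not inflated. The model SE may be wider than it needs to be, by about 1% at most, with up to about 0.9 points of power lost. The required sample size does not change.

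The 4.7% comes directly from the SAP. The 1% and 0.9 points rest on assumed asthma shares of 20% to 40%, asthma effects of up to 4 TCS points, and a simplified one-season model. With smaller asthma effects, the difference between the two covariates is negligible.

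**What to change.** - Add the asthma stratum recorded in the IRT as a fixed effect in the MMRM for the primary and key secondary endpoints (SAP 6.2 and 9.5.2). Keep ongoing asthma as a covariate and as the subgroup variable in 6.3.1.1. The two terms overlap heavily, but that affects only their own coefficients. The treatment comparison gives up one degree of freedom.
- Leave the imputation cells defined by ongoing asthma.
- Reconcile the asthma strata named in SAP 6.3.1.3 with the statement in 6.5, so that each model names the asthma variable it uses.
- State in SAP 9.5.8 whether the third convergence step, which removes ongoing asthma, leaves the stratum in the model.
- Report stratum against ongoing asthma as a two-way table by arm, so that any mismatch in the other direction and the actual balance are visible.

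The cost is one class variable, one table and a few lines of SAP text. No new data are needed.
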